7.2.10 Compaction Assessment in Morulas

Embryos that have not reached the blastocyst stage on Day 5, but are morulas, will also be evaluated. Morulas will be categorized as 1 of the following 3 options:

- Compacted: complete compaction. Tightly compacted cells. Individual cell membranes are no longer visible.
- Compacting: early stage. Cells can be distinguished.

Abnormal compaction: regional or partial compaction, or few cells (<8) in compaction

Day 5 morulas may be considered for extended culture as per the investigator/site standard of care. Day 6 or Day 7 viable blastocysts can then undergo trophectoderm biopsy and vitrification. All expanded blastocysts with Blastocyst Expansion and Hatching Status 3-6, Inner Cell Mass grading A or B, and Trophoectoderm Grading A, B, or C. should be biopsied.

The quality of Day 6 or Day 7 embryos should be assessed and recorded on the eCRF according to the criteria specified in section 7.2.9.

Date: 10 Dec 2015 E-Protocol Amendment-19588; Ver. 1.0 Supersedes: 28 October 2015 Page 43 of 69

8 ADVERSE EVENTS

8.1 Adverse Event Definition

An AE is any untoward medical occurrence in a subject participating in a clinical trial. It includes:

Trial Code: 000205

- Any unfavorable and unintended sign, symptom, or disease temporally associated with the use of the IMP, whether or not considered to be caused by the IMP.
- AEs commonly observed and AEs anticipated based on the pharmacological effect of the IMP.
- Any laboratory abnormality, vital sign, or finding from physical or gynecological examination assessed as clinically significant by the Investigator (findings from assessments and examinations done during screening are not AEs, but are recorded as medical history).
- Accidental injuries, reasons for any change in medication (drug and/or dose), reasons for any medical, nursing, or pharmacy consultation, or reasons for admission to hospital or surgical procedures.
- Overdoses and medication errors with and without clinical consequences.

8.2 Collection and Recording of Adverse Events

8.2.1 Collection of Adverse Events

The Investigator must monitor the condition of the subject throughout the trial from the time of obtaining informed consent until the last visit (EOT).

The sources of AEs cover:

- The subject's response to questions about her health (a standard non-leading question such as "How have you been feeling since your last visit?" is asked at each visit).
- Symptoms spontaneously reported by the subject.
- Investigations and examinations where the findings are assessed by the Investigator to be clinically significant changes or abnormalities.
- Other information relating to the subject's health becoming known to the Investigator (e.g., hospitalization).

8.2.2 Recording of Adverse Events

The Investigator must record all AEs in the AE Log provided in each subject's eCRF with information about:

- AE description.
- Date and time of onset (time can be omitted, if not applicable).
- Intensity.
- Causal relationship to IMP.

Trial Code: 000205

Date: 10 Dec 2015

E-Protocol Amendment-19588; Ver. 1.0

Supersedes: 28 October 2015

Page 44 of 69

- Action taken to IMP.
- Other action taken.
- Date and time of outcome (time can be omitted, if not applicable).
- Outcome.
- Seriousness.

Each of the items in the AE Log is described in detail in the following sections.

Adverse Event

Adverse events should be recorded as diagnoses, if available. If not, separate signs and symptoms should be recorded. One diagnosis/symptom should be entered per record.

If a subject suffers from the same AE more than once and the subject recovers in between the events, the AEs should be recorded separately. If an AE changes in intensity, a worst-case approach should be used when recording the event, i.e., the highest intensity and the longest duration of the event.^a

Note the following: a procedure is not an AE; the reason for conducting the procedure is. Hospitalization is not an AE; the reason for hospitalization is. Death is not an AE, but the cause of death is (an exception is sudden death of unknown cause, which is an AE).

Date and Time of Onset

The date of onset is the date when the first sign(s) or symptom(s) were first noted. If the AE is an abnormal clinically significant laboratory test or outcome of an examination, the onset date is the date the sample was taken or the examination was performed.

Intensity

The intensity of an AE must be classified using the following 3-point scale:

Mild: Awareness of signs or symptoms, but no disruption of usual activity.

Moderate: Event sufficient to affect usual activity (disturbing).

Severe: Inability to work or perform usual activities (unacceptable).

Exception: if an AE with onset before the first IMP administration (i.e., a pre-treatment AE) changes in intensity, this must be recorded as 2 separate events. The initial AE should be recorded with outcome "not yet recovered" and the date and time of outcome is when the intensity changed. The second AE should be recorded with date and time of onset when the intensity changed.

Trial Code: 000205

Date: 10 Dec 2015 E-Protocol Amendment-19588; Ver. 1.0 Supersedes: 28 October 2015 Page 45 of 69

Causal Relationship to IMP

The possibility of whether the IMP caused the AE must be classified as 1 of the following:

Reasonable possibility: There is evidence or argument to suggest a causal relationship

between the IMP and the AE. The AE may occur as part of the pharmacological action of the IMP or may be unpredictable in its

occurrence.

Examples:

- AEs that are uncommon but are known to be strongly associated with IMP exposure.
- AEs that are not commonly associated with IMP exposure, but the event occurs in association with other factors strongly suggesting causation, such as a strong temporal association or the event recurs on rechallenge.

No reasonable possibility: There is no reasonable evidence or argument to suggest a causal

relationship between the IMP and the AE.

Examples:

- Known consequences of the underlying disease or condition under investigation.
- AEs common in the trial population, which are also anticipated to occur with some frequency during the course of the trial, regardless of IMP exposure.

Action Taken to IMP

The action taken to the IMP in response to an AE must be classified as 1 of the following:

- No change (medication schedule maintained or no action taken).
- Withdrawn.
- Interrupted.
- Dose reduced.
- Dose increased.

Other Action Taken

Adverse events requiring therapy must be treated with recognized standards of medical care to protect the health and well-being of the subject. Appropriate resuscitation equipment and medicines must be available to ensure the best possible treatment of an emergency situation.

If medication is administered to treat the AE, this medication should be entered in the Concomitant Medication Log.

Date: 10 Dec 2015 E-Protocol Amendment-19588; Ver. 1.0 Supersedes: 28 October 2015 Page 46 of 69

Date and Time of Outcome

The date and time (time can be deleted/omitted, if not applicable) the subject recovered or died.

Trial Code: 000205

Outcome

The outcome of an AE must be classified as 1 of the following:

- Recovered (fully recovered or the condition has returned to the level observed at initiation of trial treatment).
- Recovered with sequelae (resulted in persistent or significant disability/incapacity).
- Recovering.
- Not yet recovered.
- Fatal.

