5.1.2 Non-Investigational Medicinal Products (NIMPs)

The NIMPs include the following.

- Ganirelix® (ganirelix acetate injection), manufactured by Merck, will be provided as a pre-filled syringe (0.5 mL) delivering 0.25 mg Ganirelix. A daily dose of 0.25 mg will be continued throughout the gonadotropin treatment period.
- Ovidrel[®] (choriogonadotropin alfa), manufactured by EMD Serono Inc., will be provided as a pre-filled syringe (0.5 mL) delivering 250 µg choriogonadotropin alfa, to be administered as a single injection as soon as 3 follicles of ≥17 mm are observed on TVUS.
- ENDOMETRIN® (Progesterone), manufactured by Ferring Pharmaceuticals Inc., will be provided as inserts to be administered vaginally. On the day that the progesterone inserts are initiated, only a single, 100 mg dose of ENDOMETRIN® will be given. On subsequent days, ENDOMETRIN® will be administered 2 times daily, each delivering 100 mg of Progesterone (200 mg/day). ENDOMETRIN® will be initiated the evening of the day after oocyte retrieval and will continue until the day of the second β -hCG test (if negative) or if pregnancy is confirmed by the second β -hCG test for a maximum of 10 weeks total.

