5.4 Conditions for Storage and Use

The Investigator will ensure that the medicinal products will be stored in appropriate conditions in a secure location with controlled access as per the label for each drug. The storage compartment shall be monitored regularly with a minimum-maximum thermometer and the values shall be documented. Deviations in storage temperature must be reported to the Sponsor without delay and the IMP must not be used until acceptance from the Sponsor is received. See package inserts for specific storage and use instructions of MENOPUR® (menotropins for injection [package insert] 2014), Gonal-f RFF® Redi-jectTM (follitropin alfa injection [package insert] 2014), Ganirelix® (ganirelix acetate injection [package insert 2013]), Ovidrel® (choriogonadotropin alfa [package insert] 2014), and ENDOMETRIN® (Progesterone) [package insert] 2014).

The IMPs (MENOPUR® or Gonal-f®) will only be administered to subjects who meet the eligibility criteria and are randomized to a treatment group in the study.

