8.4.2 Collection, Recording and Reporting of Serious Adverse Events

SAE Reporting by the Investigator

All SAEs must be reported immediately to the contract research organization (CRO) and/or Ferring Pharmaceuticals as soon as it becomes known to the Investigator and not later than within 24 hours of their knowledge of the occurrence of an SAE.

The Investigator is responsible for submitting the completed SAE Report Form with the fullest possible details to the CRO and/or the local safety officer at Ferring Pharmaceuticals, Inc. by fax within 24 hours of his/her knowledge of the SAE and submit all related follow-up information no later than 3 calendar days using the contact details below:

Completion of the Demographics Log, AE Log, Medical History Log, and Concomitant Medication Log is mandatory for initial reports and for follow-up reports if any changes have been made since the initial report.

Additional information relevant to the SAE such as hospital records, results from investigations, e.g., laboratory parameters (that are not already uploaded in the eCRF), invasive procedures, scans and x-rays, and autopsy results can be faxed or scanned and e-mailed to Ferring Pharmacovigilance using the contact details in the section above. In any case, this information must be supplied by the Investigator upon request from Ferring. On any copies provided, details such as the subject's name, address, and hospital identification number should be concealed and instead the subject number should be provided.

The Investigator will supply Ferring and the IRB with any additional requested information, such as results of post-mortem examinations and hospital records.

Expedited Reporting by Ferring

Ferring will report all AEs that are serious, unexpected, and with a reasonable possible causality to the IMP, as judged by either the Investigator or Ferring, to the relevant parties within the stipulated timelines.

The expectedness is assessed by Ferring according to the Package Inserts for both the IMP and Non IMP products.

Serious AEs will be considered reportable regardless of whether or not the IMP or Non IMP was used in accordance with the provisions in the protocol, Package Inserts, and labeling.

Date: 10 Dec 2015 E-Protocol Amendment-19588; Ver. 1.0 Supersedes: 28 October 2015 Page 49 of 69

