9.8.2 Adverse Events

Adverse events will be coded using MedDRA.

A treatment-emergent AE is defined as an AE that emerges during treatment having been absent pre-treatment, or worsens relative to the pre-treatment state. Only treatment-emergent AEs will be presented in summary tables.

All data will be listed per subject and AE.

Written narratives will be issued for all SAEs and AEs leading to withdrawal. If causality is missing, the AE will be regarded as being reasonably possibly related to IMP. Related AEs (judged as being reasonably possibly related to IMP) will be termed adverse drug reactions.

Overview of Treatment Emergent Adverse Events

A treatment-emergent AE summary table will be presented, including for each treatment, the number of subjects reporting an AE, the percentage of subjects with an AE, and the number of events reported, for the following categories:

- All AE.
- Severe AEs
- Adverse drug reactions.
- AEs leading to discontinuation.
- SAEs.
- Deaths.

Incidence of Adverse Events

Treatment-emergent AEs in each treatment group will be tabulated by system organ class (SOC) and preferred term. The following will be presented: number of subjects reporting an AE, the percentage of subjects with an AE, and the number of events reported.

For each treatment the following counts are done:

- For number of subjects experiencing a particular event, counting will be done by subject and not by event. This is valid for both the SOC and preferred term, i.e., a subject will only be counted once in each SOC and once within each preferred term.
- For total number of events counting will be done by event. This is valid for both the SOC and preferred term, i.e., an event occurring more than once for the same subject will be counted for each occurrence.

E-Protocol Amendment-19588; Ver. 1.0 Supersedes: 28 October 2015 Page 56 of 69

Date: 10 Dec 2015

This counting and data presentation will be applied for the various incidences of AE tables described below.

Incidence of OHSS

OHSS for each treatment group will be tabulated by classification (mild, moderate, severe) and grade (1, 2, 3, 4, 5). The tabulation will be made for OHSS overall as well as separately for early OHSS and late OHSS.

Incidence of AEs by Relationship to IMP

Treatment-emergent AEs for each treatment group will be tabulated by SOC, preferred term, and relationship to IMP. One summary table will be prepared per type of relationship (related/not related).

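### Causality is asked for the IMP only, so a serious unexpected reaction attributed solely to a non-IMP falls outside the sponsor's expedited rule and the adverse drug reaction tables

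*Protocol*

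**What the plan says.** **Products.** Protocol Section 5.4 identifies the IMPs: "The IMPs (MENOPUR® or Gonal-f®) will only be administered to subjects who meet the eligibility criteria". Section 5.1.2 introduces the other products with "The NIMPs include the following" and names ganirelix, Ovidrel and ENDOMETRIN. Leuprolide acetate is not on that list, but Sections 3.1.2 and 6.4 specify it as the trigger after an excessive response. IMP dosing lasts at most 20 days. ENDOMETRIN starts after oocyte retrieval and continues "if pregnancy is confirmed by the second β -hCG test for a maximum of 10 weeks total".

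**Recording.** The AE log in Section 8.2.2 has one causality item, "The possibility of whether the IMP caused the AE must be classified as 1 of the following", with two answers, both about the IMP. The action item has the same scope: "The action taken to the IMP in response to an AE must be classified as 1 of the following". A further item, for other action, describes only how the event itself is treated.

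**Expedited reporting.** Under Section 8.4.2 the sponsor "will report all AEs that are serious, unexpected, and with a reasonable possible causality to the IMP", on the judgement of either the investigator or the sponsor. The same section then says: "The expectedness is assessed by Ferring according to the Package Inserts for both the IMP and Non IMP products".

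**After the last visit.** Section 8.5.1 requires continued follow-up of events that are serious or possibly caused by the IMP. Section 8.5.2 requires a report of an SAE that comes to light after the last visit if the investigator links it to the IMP.

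**Tabulation.** Protocol Section 9.8.2 states: "Related AEs (judged as being reasonably possibly related to IMP) will be termed adverse drug reactions". SAP Sections 10.2.1 and 10.2.2 use the term without redefining it.

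**The concern.** The expectedness sentence in Section 8.4.2 suggests that reactions to the non-IMPs were meant to be within reach of expedited reporting. The causality condition in the same section takes them out again, and the AE log collects no judgement that could bring them back. An investigator who believes that a reaction is due to ganirelix, the trigger or luteal support alone has nowhere to say so, and the accurate answer to the only question asked is that the IMP did not cause it.

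These products are given because the protocol requires them, and ENDOMETRIN continues after the IMP has stopped. At stake is whether a serious unexpected reaction to one of them is passed on under the sponsor's own rule, whether it can be found in the safety tables as a drug reaction, and whether it is pursued once the subject has left the trial.

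**Working it through.** No arithmetic applies. The check is to follow one hypothetical event through each rule, first when it is attributed solely to a non-IMP and then when both an IMP and a non-IMP are suspected.

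| Step | Source | Non-IMP only | Both suspected |
|---|---|---|---|
| Causality code in AE log | Protocol 8.2.2 | No reasonable possibility | Reasonable possibility |
| In-trial SAE sent to CRO and/or sponsor within 24 hours | Protocol 8.4.2 | Yes | Yes |
| Expectedness checked against non-IMP insert | Protocol 8.4.2 | Yes | Yes |
| Sponsor's expedited criterion, if serious and unexpected | Protocol 8.4.2 | Not met | Met |
| SAE narrative, table and listing | Protocol 9.8.2; SAP 10.2.2 | Included | Included |
| Counted as adverse drug reaction | Protocol 9.8.2; SAP 10.2.1, 10.2.2 | No | Yes |
| Non-serious event unresolved at last visit | Protocol 8.5.1 | Follow-up not required | Follow-up required |
| SAE learned of after last visit | Protocol 8.5.2 | Report not required | Report required |

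The expedited rule joins three conditions: serious, unexpected, and possible causality to the IMP. If the third fails, the event is not reported whatever the insert says. The non-IMP insert therefore cannot by itself make an event reportable.

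Four other provisions were checked to see whether they close the gap:

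- Section 8.4.2 has a further sentence naming non-IMPs. It says that reportability does not depend on whether a product was used in line with protocol and labeling. It does not change the causality condition.
- SAP Section 10.2 treats a missing causality as related to the IMP. This works only when the item is left blank, not when it is answered accurately.
- Protocol Section 8.4.1 requires deaths within 4 weeks after treatment ends to be reported whatever the relation to the IMP. This is a genuine exception to the last row, but only for deaths.
- Protocol Section 6.9 collects pregnancy losses and congenital anomalies during follow-up of ongoing pregnancies. It records outcomes and does not ask about product causality.

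**The case against.** The strongest reply is that little is hidden. Every in-trial SAE goes to the CRO and/or sponsor within 24 hours with the concomitant medication log. It gets a narrative and is tabulated and listed. During the trial every AE is followed until it resolves or stabilizes, and serious ones are followed after the last visit too. The sponsor may make its own causality judgement. The trial compares two gonadotropins on shared background drugs, so defining adverse drug reactions by the IMP is a defensible choice. The documents also do not define the recipients or timelines of onward reporting, so they cannot show that any external duty is breached.

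Most of this stands and limits the point. It does not answer it: the sponsor's judgement under Section 8.4.2 is still about the IMP, the mismatch within that section remains, and the 24-hour rule does not settle what happens after the last visit, where Section 8.5.2 sets its own IMP-only condition.

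A reader might infer more, and the documents do not support it:

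- *That suspecting a non-IMP forces a negative IMP code.* It does not. The negative code requires that there be no reasonable argument for an IMP link, so shared suspicion is still captured.
- *That the tables of AEs leading to discontinuation or withdrawal miss these events.* Neither Protocol Section 9.8.2 nor SAP Sections 10.2.1 and 10.2.2 builds them from the IMP action item. An AE that led a subject to leave the study fits them as worded.
- *That OHSS results are distorted.* OHSS is tabulated by severity and timing whatever its attributed cause (Protocol 9.8.2, SAP 10.5.1), and no dedicated related/unrelated comparison of OHSS is planned.
- *That cancelled fresh transfers, or a non-IMP stopped for an AE, should count as withdrawals.* Neither means that the subject has left the study, and SAP Section 10.5.2 already counts cancellations for excessive response and leuprolide use.

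**Conclusion.** The point holds for events attributed solely to a non-IMP. As written, such an event fails the sponsor's expedited criterion even when serious and unexpected, and is not counted as an adverse drug reaction. After the last visit it need not be reported if serious (deaths within 4 weeks after treatment ends excepted), and need not be followed if non-serious. The IMP-only action item has the same narrow scope, but nothing in either document is shown to depend on it.

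The size is a class of events, not a number. The documents give no rate for non-IMP reactions. It is tempting to use the share of treatment days that falls after the IMP has stopped, but that is calendar time under maximum ENDOMETRIN use in pregnant subjects. It says nothing about how many reactions occur or are misclassified.

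The conclusion assumes that sites and sponsor follow the wording exactly and that no other document, such as a safety management plan, adds a non-IMP causality assessment. It bears on safety reporting and does not touch the primary analysis. It is a modest but worthwhile correction.

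**What to change.** 1. **Protocol 8.2.2 and the eCRF.** Add one causality item with the same two answers for any protocol-mandated non-IMP, naming ganirelix, Ovidrel, leuprolide and ENDOMETRIN. Leuprolide has to be named because Section 5.1.2 does not list it.
2. **Protocol 8.4.2, 8.5.1 and 8.5.2.** Extend the causality condition to read *causality to the IMP or a non-IMP*. In 8.4.2, judge expectedness against the insert of the suspected product. Section 17 cites no leuprolide insert, so add one.
3. **SAP 10.2.1 and 10.2.2.** Keep the adverse drug reaction summaries as defined for the IMP, and add one row for events related to a non-IMP.

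The cost is one eCRF field, aligned wording in three protocol sections, one table row and a few more expedited reports. No dose, schedule or clinical rule changes.

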8.3 Pregnancy and Pregnancy Outcome

Subjects who achieve pregnancy (2 positive β -hCG tests) will be followed for clinical pregnancy (intrauterine gestational sac and/or fetal heart movement approximately 4-5 weeks after embryo transfer) and ongoing pregnancy (approximately 8-9 weeks after embryo transfer). Pregnant subjects will complete their final study visit approximately 8-9 weeks after embryo transfer (or sooner, if there is a loss of pregnancy). Subjects with ongoing pregnancy will be followed by telephone or mail for live birth data and information will be recorded in the eCRF. Pregnancy loss will be recorded on a pregnancy follow-up form in the eCRF.

Trial Code: 000205 Date: 10 Dec 2015 E-Protocol Amendment-19588; Ver. 1.0

Supersedes: 28 October 2015 Page 47 of 69

